Monopolar Survey: The DBS device is activated approximately one month after surgery as part of routine care in a session called the monopolar survey. Because of the special design of the directional lead used in this study, the monopolar survey will take longer than that for routine care. In this encounter we will optimize the participant's DBS as if it were a conventional DBS system. We will also assess the therapeutic window of each electrode contact. Therapeutic window is a useful continuous measure of the available range of DBS intensities at a given stimulation site that provides motor improvement without intolerable side effects. For our purposes, the floor of the therapeutic window is defined as the lowest stimulus amplitude that markedly improves arm rigidity, whereas the ceiling amplitude elicits either involuntary contraction of the contralateral mouth or arm because of corticospinal activation or noticeably worsens PD symptoms.

Crossover Study: In a balanced design, we will randomly allocate patients to three different conditions, each over two month intervals, (1) conventional DBS guided by behavioral testing

(UPDRS, pegboard dexterity, gait speed test, and dynamic balance/posture measures (see motor battery above for descriptions)), (2) multiple active contacts selected based on behavioral testing, and (3) multiple contacts selected by cortical physiology alone. In the first month of each randomization period, participants will be allowed to adjust stimulus amplitude at home, within safety limits defined by therapeutic window measures from the monopolar survey. Patient adjustment of DBS settings at home has been part of routine care for years. They will remain on this preferred amplitude for the second month of the randomization period and then return at the end for motor and non-motor assessments. Motor outcomes for the crossover will include repeat UPDRS part 3, pegboard dexterity, gait speed test, and posture/balance measures from the Motor Battery (discussed previously).

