d. If different phases are involved, what is the duration of each phase in which the participants will be involved? If no phases are involved, enter "not applicable."

Pre-op baseline evaluation: Involves two study visits. One is a motor battery (see 16a above) visit lasting approximately one hour and the other is one cognitive/speech/quality of life evaluation (see 16a above) lasting approximately 3 hours. The pre-op baseline evaluation will take place during month one following enrollment.

DBS implantation surgery: Typical DBS surgeries last between 2-3 hours. Here we will measure cortical activation by DBS with EEG/ECOG/EMG. The actual research portion on the day of surgery will extend the surgical time by no more than 30 minutes. As per routine care, O-arm CT images and post-op MRI images that we will use for DBS lead localization will be gathered as well. DBS electrode implantation surgery will take place during month 2 following enrollment.

Monopolar survey: Here the participant's DBS will be activated and therapeutic settings will be identified. This involves a clinical visit and lasts approximately two hours. In addition, we will assess the participant's movement abilities with our motor battery (see 16a above) lasting approximately one hour. The monopolar survey will take place during month 3 following enrollment.

Crossover study: This portion of the study will involve six separate study visits over the course of 6 months to evaluate three different DBS stimulation conditions. For each condition we will assess our motor battery and field shaping surveys in one visit (see 16a above) lasting approximately one hour and our cognitive/speech/quality of life batteries (see 16a above) in one visit lasting approximately 3 hours. Also, see Table 3 below.

TABLE 3. Summary of research encounters, procedures, and corresponding specific aims.	Pre-op baseline	DBS surgery	Monopolar Survey	Double-blind, randomized crossover to omnidirectional versus directional DBS guided by monopolar survey				Crossover to directional DBS guided by EEG/ECoG	Study exit at 1 year with repeat EEG		
				Condition 1		Condition 2					
Specific Aim(s)	All		1.1 and 1.2		2.1, 2.2, and 2.3						
Encounter number	1a	1b	2	3	4a	4b	5a	5b	6a	6b	7
Encounter duration (hours)	1	3	3-4	3	3	3	3	3	3	3	3
Calendar duration (months)	1		2		3 to 4		5 to 6				12
Medication state	off	on	off	off	on	off	on	off	on	off	off
Motor battery											
Cognitive/behavioral battery											

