SA1. To test the hypothesis that specific contacts on a novel segmented DBS lead in the STN region activate functionally distinct populations of cortical axons within individual PD patients. SA1.1 will measure within-participant contrasts in therapeutic window and UPDRS part 3 change versus pre-op baseline across the different segments on the directional DBS lead with two-way repeated measures mixed models using Proc Mixed in SAS, with conventional versus current steering DBS contacts as factors and therapeutic window and change in UPDRS part 3 as data. The primary outcome measure for SA1.2 will compare whether intraoperative ERPs predict within-participant changes in the clinical outcomes from SA1.1. We will contrast the ERPs within and across stimulation sites with two-way repeated measures mixed models using Proc Mixed in SAS, with stimulus amplitude, location, and recording modality (EEG or ECOG) as factors and P1/N1 latency and HFO integrated area as data. Using linear contrasts from the regressions, we will directly compare whether EEG and ECOG measures of DBS amplitude thresholds (1) that change P1/N1 latency and (2) elicit the large amplitude HFOs better predict the size of the therapeutic window for a given DBS electrode contact. Secondary outcomes will correlate these amplitude thresholds with changes in the UPDRS part 3 score, UPDRS subscores, and other elements of the Motor battery measured in SA1.1. To control for potential subclinical corticospinal tract activation, we will report the latency and magnitude of EMG response(s) in the contralateral arm and leg muscles using residual analyses, when and if these responses are present. Sample size for SA1. Our preliminary findings show robust within- and between-subject changes in ERP latency that predict postoperative motor side effects. For the first primary outcome, a sample size of 18 will have 80% power to detect a difference between a null hypothesis regression slope of 0 and an alternative regression slope of 0.3 or higher standardized units, assuming that the standard deviation of the predictor variable, DBS amplitude threshold, is 2.370 mA (the standard deviation of the stimulus intensities) and the standard deviation of the normalized residuals ($sd=1$) of the therapeutic window using a t-test with a 0.05 two-sided significance level. Thus, we will be overpowered for SA1, because a large sample of 30 is dictated by SA2.3. As an additional secondary analysis, we will compare the predictive power of EEG versus ECOG, we will first regress the primary outcomes on EEG and then determine how much of the residual variance is explained by ECOG. If EEG explains 50% of the variance in the primary outcome, then we will have 80% power to detect an increase in the R-square of 8.6%. If the additive R-square of EEG is 25%, we will have 80% power to detect an increase of 12.9%. If we cannot demonstrate superiority of ECOG, we would default to the less invasive modality. We will look at the assumptions of the model by examining the residual plots in the regression models for both modalities.

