selected based cortical ERP physiology, using both therapeutic window and change in UPDRS part 3 as data nested within person. Secondary analyses will contrast the efficacy of these DBS adjustment strategies based upon changes in other elements of the Motor battery. In SA 2.3, we use the randomized, doubleblind crossover trial to compare changes in UPDRS and other measures of quality of life and motor, cognitive, behavioral, and speech function across the DBS programming strategies identified in SA 2.1. The primary statistical analysis will use Proc Mixed in SAS with active contact groupings including (1) conventional DBS, (2) multiple active contacts selected based on behavior, and (3) multiple active contacts based on ERPs as factor and patient preference and changes in PDQ-39 and UPDRS part 3 as data. Sample size for SA2. We will obtain multiple repeated measures within participants and can readily detect changes in patient preference, PDQ-39, UPDRS part 3, and other motor and non-motor variables of interest. Patient reported evidence for the hypothesis of superiority of current steering will be shown by determining that 20 or more of the 30 participants favor either current steering approach over conventional DBS using a binomial distribution based on patient preference (vote), PDQ-39, and UPDRS part 3. This would achieve a p value of < 0.049 . We will declare current steering DBS to be clinically superior to conventional therapy based on patient preference if 20 or more patients meet this criterion. We will measure the frequency by which current steering provides better outcomes versus conventional DBS, which could still be highly relevant and significant clinically (even if preferred by <20 participants). Secondary measures will quantify within-participant changes in upper limb dexterity, gait speed test, posture and balance, cognitive/behavioral measures, speech, and motor diaries. Additionally, we will contrast the probability that active contacts are shared among the programming strategies (conventional DBS, current steering guided by behavior, and current steering guided by cortical physiology). The extent to which contacts and stimulation parameters are shared among these approaches could be informative and provide a useful internal validation of the current steering approach.

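### The SA 2.3 primary model has no period term, which costs power for conditions given in randomised order; how much, and whether the term can be fitted for the ERP arm, depends on an order that the protocol states two ways

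*SAP*

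**What the plan says.** **Model.** The SAP, under SA2, describes the SA 2.3 analysis: "The primary statistical analysis will use Proc Mixed in SAS with active contact groupings including (1) conventional DBS". The other two groupings are contacts chosen on behaviour and contacts chosen on ERPs. The sentence ends "as factor and patient preference and changes in PDQ-39 and UPDRS part 3 as data". Neither document names a period, sequence or carryover term.

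**Size and decision rule.** The SAP's SA1 text says that "a large sample of 30 is dictated by SA2.3". Superiority is declared if "20 or more of the 30 participants favor either current steering approach over conventional DBS using a binomial distribution". The SAP adds: "This would achieve a p value of < 0.049". It gives no power figure for the mixed model.

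**Order of conditions.** The protocol gives two accounts.
- Section 16.a, Crossover Study: "In a balanced design, we will randomly allocate patients to three different conditions, each over two month intervals".
- Section 16.d, Table 3: one column group is headed "Double-blind, randomized crossover to omnidirectional versus directional DBS guided by monopolar survey" and holds Conditions 1 and 2. A later column is headed "Crossover to directional DBS guided by EEG/ECoG".

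Other text agrees with Table 3. Section 16.a puts the field shaping surveys at the end of the first two conditions and bases the electrophysiology-guided arm on their results. The rationales of Milestones 2.6 and 4.3 (section 23) describe that arm as the last one.

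**The concern.** Periods in this trial may well differ systematically. The device is first activated about a month after surgery and the two-month periods follow. Patients adjust their own amplitude in the first month of each period. Section 18.c says that DBS often lowers the need for dopaminergic drugs, and Table 3 schedules the quality-of-life battery on medication. The motor and quality-of-life batteries are repeated at each crossover assessment.

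A crossover lets the analyst remove such drift. With condition as the only factor, it is not removed. In balanced random order it does not shift the condition estimates, but it inflates the residual, so power for PDQ-39 and UPDRS part 3 is lost. If the completed orders become unbalanced, part of the drift enters the contrast as bias. Both accounts of the order randomise conventional versus behaviour-guided DBS, so the omission matters for that comparison in either case.

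**Working it through.** **The plan's own figure.** The only figure given for SA 2.3 is for the vote: P(X ≥ 20 | n = 30, p = 0.5) = 0.0494, one-sided. This matches the stated 0.049 to three decimals. It contains no residual variance, so it says nothing about the model.

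**Inputs.** From the documents: 30 patients, three conditions, three periods, condition as the only factor, patient as the repeated unit. Assumed: complete data, within-patient residual SD of 1, no carryover, linear drift of d per period (0, d, 2d), two-sided 0.05. The range d = 0.25 to 1 is illustrative.

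**Residual degrees of freedom**, condition-only model: 90 observations − 30 patients − 2 for condition = 58.

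**Layout A: all three conditions balanced over periods** (six orders, five patients each). Every condition has mean drift d, so contrasts are unbiased. Each patient leaves residuals −d, 0 and d, a sum of squares of 2d². Over 30 patients this is 60d². Expected residual mean square = (58 + 60d²)/58, a relative rise of 60d²/58.

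**Layout B: ERP always third, the other two balanced over periods 1 and 2.** Mean drift is 0.5d for conventional, 0.5d for behaviour-guided and 2d for ERP. Each patient leaves residuals of ±0.5d on the first two conditions and 0 on ERP, a sum of squares of 0.5d². Over 30 patients this is 15d², a relative rise of 15d²/58.

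**Power.** Take an effect that gives 80% power without drift: 0.736 SD, which is 2.85 standard errors, since 0.736/√(2/30) = 2.85. The estimate's true variance is unchanged, but the test divides by an inflated SD, so the critical value of 2.00 is in effect multiplied by the square root of the variance ratio. Example, layout A at d = 0.5: √1.259 = 1.122; 2.00 × 1.122 = 2.24; 2.85 − 2.24 = 0.61, which gives about 73%.

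| d | A: variance rise | A: power | A: type I error | B, conventional vs behaviour-guided: variance rise | B: power | B: type I error |
|---|---|---|---|---|---|---|
| 0.25 | 6% | 78% | 4.3% | 2% | 80% | 4.8% |
| 0.5 | 26% | 73% | 2.8% | 6.5% | 78% | 4.3% |
| 1 | 103% | 50% | 0.6% | 26% | 73% | 2.8% |

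Simulations of both layouts agree within simulation error. With a period term in layout A, power is about 80% and type I error about 5% at every d.

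**ERP contrasts in layout B.** ERP minus conventional, and ERP minus behaviour-guided, are biased by 2d − 0.5d = 1.5d: 0.375, 0.75 and 1.5 SD. Simulated type I error for ERP versus conventional is about 30%, 80% and 100%. Condition plus period has rank 3 out of 4, because period 3 and the ERP condition are the same column. No period adjustment is available for these contrasts.

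**Unbalanced orders.** As a deliberately large example for the randomised pair, suppose 18 completers had conventional first and 9 had it second. The bias is (18d − 9d)/27 = d/3, or 0.17 SD at d = 0.5 and 0.33 SD at d = 1. A period term removes it.

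**The case against.** **The drift is assumed.** This stands. No figure is given, and at d = 0.25 the loss is trivial in either layout. PDQ-39 and UPDRS part 3 are assessed after a month at fixed amplitude, which may limit drift. The clearest practice effects would fall on pegboard and cognitive tests, which are secondary.

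**The SAP sentence may simply be brief.** Possible, but for SA1 and for SA 2.1 and 2.2 the SAP specifies two-way repeated-measures models, whereas for SA 2.3 it names one factor. Followed as written, the analysis has no period term.

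**The declared success rule is the 20-of-30 vote.** True, and it uses no residual variance. Adding a period term to the model neither improves nor harms it.

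**A reader might infer more than the documents support.**
- That all drift goes into the error and every condition test is conservative. This needs all three conditions balanced over periods, which only the Crossover Study text in section 16.a states. If ERP is always third, the ERP tests err in the opposite direction.
- That a period term repairs every contrast. It cannot do so for ERP in a fixed last position.
- That sequence and pre-operative value must also be fitted. Both are constant within a patient, so with complete data they do not change within-patient contrasts.

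**Conclusion.** The omission is real and worth correcting. For conditions in balanced random order the cost is lost power with conservative tests, not a false finding. Bias enters those contrasts only if the completed orders become unbalanced. The loss ranges from negligible at d = 0.25 to large at d = 1 if all three conditions are balanced over periods, and is a quarter of that variance rise for conventional versus behaviour-guided DBS if ERP is always third. These sizes rest on linear drift, equal within-patient variance, no carryover and 30 complete patients.

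The more serious consequence depends on the order. If the ERP condition is fixed last, its contrasts carry the drift as bias and cannot be adjusted. The documents do not settle which layout applies, so it cannot be said outright that the ERP contrasts are either conservative or biased.

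**What to change.** 1. Reconcile the Crossover Study text in protocol section 16.a with the field shaping and exploratory-arm text in the same section, Table 3 in 16.d, and Milestones 2.6 and 4.3. State one order of conditions.
2. If the order of all three conditions is randomised, fit the PDQ-39 and UPDRS part 3 models with fixed effects for condition and period and a random patient effect.
3. If the ERP condition is fixed last, fit condition and period for conventional versus behaviour-guided DBS only, and label ERP contrasts as non-randomised and confounded with period.
4. Sequence and pre-operative value may be added but are optional.

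The cost is one SAP sentence and one degree of freedom for the pair, or two for three periods. No new data are needed. The 20-of-30 preference rule is unchanged.

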During the Motor Battery assessments in the crossover, we will conduct Field Shaping Surveys to determine whether tailored activation of combinations of DBS contacts, guided by patient-specific network physiology, predicts changes in therapeutic window (the range of therapeutically effective stimulus amplitudes versus omnidirectional DBS). They will occur in the motor assessments at the conclusion of the first two crossover conditions. While in the operating room we will measure stimulus evoked activity and local field potential data through the DBS lead in response to hand, leg, and mouth movements. In addition to the primary study outcomes comparing directional versus omnidirectional DBS, we will use these encounters to determine if specific combinations of DBS contacts, guided by stimulus evoked activity and local field potentials in surgery, improve motor symptoms. Behavioral measures will include therapeutic window, MDS-UPDRS Part III, pegboard dexterity, gait speed test, and dynamic balance/posture measures (see motor battery above for descriptions) across different combinations of contacts on the segmented lead.

Non-motor assessments will occur on a different day and include patient-reported quality of life measures, cognitive/behavioral, and speech batteries (discussed previously). At study conclusion, we will conduct an open-ended exit interview to ask patients about their overall experience, to rank the programming strategies from the crossover study from best to worst, and explain their rationale for the rankings.

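### The documents conflict on whether ERP-guided DBS is a randomized crossover condition; if it always comes third, the SAP's three-level model reports a contrast confounded with period as randomized evidence

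*SAP*

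**What the plan says.** **Three randomized conditions.**
- SAP, SA2: the primary analysis for SA 2.3 uses one treatment factor with the levels "1) conventional DBS, (2) multiple active contacts selected based on behavior, and (3) multiple active contacts based on ERPs as factor". The SAP presents this as the randomized, double-blind crossover. It names no period or sequence term and gives the ERP level no separate status.
- Protocol 16a, Crossover Study: "In a balanced design, we will randomly allocate patients to three different conditions, each over two month intervals", the third being contacts chosen by cortical physiology.
- Protocol 16d, Crossover study text: six visits "over the course of 6 months to evaluate three different DBS stimulation conditions".

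**Two randomized conditions, with ERP apart.**
- Protocol 16d, Table 3 header: "Double-blind, randomized crossover to omnidirectional versus directional DBS guided by monopolar survey", with the EEG/ECoG-guided crossover listed separately. Only the header is relied on here, since the table body does not read reliably.
- Protocol 16a and 16d, Exploratory Crossover Arm: both headings call the ERP arm exploratory. The 16a text compares it with the randomized crossover as with something else, and the 16d text calls it nested.
- Protocol 23, Milestones 2.6 and 4.3 (rationales): it is the final arm or condition.
- Protocol 16a, on the Field Shaping Surveys: "In addition to the primary study outcomes comparing directional versus omnidirectional DBS".

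**The survey.** Protocol 16a (Exploratory Crossover Arm) and Milestone 2.6 make the field shaping survey an input to the ERP settings. The SAP makes the SA 2.1/2.2 testing an input to current steering in SA 2.3. The stated timings differ:
- Milestones 2.6 and 4.3: once the second treatment period is over.
- Protocol 16a: "They will occur in the motor assessments at the conclusion of the first two crossover conditions".
- Protocol 16d: "For each condition we will assess our motor battery and field shaping surveys in one visit".

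**The concern.** Whether ERP-guided programming helps is the trial's central question. If its place in the sequence is fixed, ERP minus conventional compares a last period with earlier ones, and anything that changes over time enters the estimate. Growing experience with home amplitude adjustment could do this, as could recency when patients are asked "to rank the programming strategies from the crossover study from best to worst". Because the SAP's model has no period term, the software would return an ERP estimate without any warning, and the SAP's wording would present it as randomized and double-blind. The SAP's superiority declaration is exposed in the same way: it needs 20 of 30 patients to prefer either of the two steering strategies, so on this reading it counts votes for an arm that always comes last.

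**Working it through.** **Notation.** A = conventional, B = behavior-guided, C = ERP-guided. There are 30 patients (SAP, SA2) and three two-month periods (Protocol 16a) with period effects p1, p2 and p3. The sequences are inferred, since no section lists them: A-B-C and B-A-C if ERP is fixed third, or all six orders with five patients each if the three conditions are randomized in a balanced way.

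**The plan's own figure.** The only number the SAP gives for SA 2.3 is the preference rule's p value, stated as below 0.049. The exact one-sided tail P(X ≥ 20 | n = 30, 0.5) is 0.0494. It describes a single 50:50 choice and says nothing about period, so it does not bear on this point.

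**1. Can the sections all be followed?** In six balanced orders, C falls in period 1 for 2 × 5 = 10 patients and in period 2 for another 10. With the survey after period 2, 10 + 10 = 20 of 30 patients would start ERP settings before the survey that is meant to inform them. On either of the other two timings, the 10 patients who start with C would do so before any survey. No timing in the documents fits full three-way randomization together with survey-informed ERP settings.

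**2. What does the SAP's model estimate if C is third?** With 15 patients per sequence and no period term:
- C − A estimates (true C − A) + p3 − (p1 + p2)/2. The same term enters C − B.
- B − A estimates (true B − A) + [(n1 − n2)/30] × (p2 − p1), where n1 and n2 are the sequence sizes. The bias is 0 at 15/15, (2/30) = 0.067 of (p2 − p1) at 16/14, and (6/30) = 0.20 at 18/12.

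**3. What is estimable once period is added?** With 30 patient, 2 treatment and 2 period columns (34 in all):

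| Design | Rank | B − A | C − A, C − B |
|---|---|---|---|
| A-B-C / B-A-C | 33 of 34 | estimable, SE √(2/30) = 0.258 residual SD | not estimable |
| Six balanced orders | 34 of 34 | estimable, SE 0.258 | estimable, SE 0.258 |

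In the first design the C column is identical to the period-3 column.

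**4. Carryover.** B − A in the two-sequence design also carries −0.5 × (carryover of B − carryover of A), with or without period terms. Its validity therefore assumes no differential carryover.

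**5. Illustration with assumed drift.** The documents give no period effect, so these sizes are assumptions. Take no true effect, a shift d in period 3 only, the SAP's model, 90 − 32 = 58 degrees of freedom, and noncentrality d/0.258:

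| d (residual SD) | C − A, ERP fixed third (two-sided rejection) | C − A, six orders, no period term |
|---|---|---|
| 0.10 | 6.7% | 4.9% |
| 0.25 | 15.9% | 4.6% |
| 0.50 | 47.8% | 4.0% |

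These are two-sided rates. At d = 0.10, 5.7% of trials reject in ERP's favour, against 2.5% with no drift. B − A stays at about 5% throughout when ERP is fixed third. In six balanced orders the drift goes into the residual: no inflation, only some loss of precision.

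**The case against.** The strongest reply is that the aliasing depends on which design governs. Protocol 16a (Crossover Study) and the SAP agree on three randomized conditions. Even the exploratory-arm section of 16a uses the language of a randomization period, and Milestone 2.6 places the arm inside the double-blind crossover. Milestone 1.5 refers to an NIH-approved design through cross-references that do not resolve in the text. This stands: the conflict is certain, the aliasing is conditional.

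Second, the protocol already labels the ERP arm exploratory and words its primary outcomes as directional versus omnidirectional. That also stands, but the label has not reached the SAP, which is where the primary model and the superiority rule are set.

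Third, practice effects fit the timed and cognitive tests, which are secondary, better than the primary data (preference, PDQ-39, UPDRS part 3). A period shift could also go against ERP. Both are fair, and they are why the drift figures are illustrations only. The aliasing needs no particular size or direction.

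Fourth, outcomes are assessed after two months on each condition, the second at a fixed amplitude, which limits carryover. This is true, although no washout is described and the assumption should be written down.

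A reader might also infer that any excess chance of meeting the 20-of-30 rule comes from ERP being last. The documents do not support that: counting a preference for either of two strategies raises the chance above that of a single 50:50 comparison even when all three conditions are randomized. That is a separate problem.

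**Conclusion.** The documents contradict each other on whether ERP-guided DBS is randomized and on when the survey that informs it takes place. This holds on any reading.

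If ERP is fixed third (orders inferred as A-B-C and B-A-C), the primary model as written puts 100% of the period-3 shift, measured against the mean of periods 1 and 2, into ERP minus conventional and reports it as a randomized, double-blind result. Adding period terms does not rescue that contrast, because it is then not estimable.

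A reader might go further and conclude that the ERP comparison is certainly confounded, or that SA 2.3 as a whole is invalid. Neither follows. With three conditions in balanced random order there is no aliasing, and the unstated period term mainly affects precision. With ERP fixed third, behavior-guided minus conventional is still a randomized comparison (SE 0.258 residual SD), given balanced sequences or a period term, and no differential carryover. The rates of 6.7%, 15.9% and 47.8% rest on assumed drifts and are not forecasts.

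The matter should be settled before analysis, because it concerns the primary SA 2.3 model and the superiority declaration.

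**What to change.** Reconcile Protocol 16a, 16d with Table 3, Milestones 2.6 and 4.3, and the SAP's SA2 section on three things: which conditions are randomized, in what order, and when the survey falls. Which design applies is for the sponsor to state.

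**If ERP is fixed third:**
- Base the randomized SA 2.3 analysis on conventional versus behavior-guided only, with treatment, period and sequence as fixed effects and patient as random. State the assumption of no differential carryover.
- Base the preference declaration on the same pair, which can be read from the exit ranking already planned.
- Report ERP against each other condition separately, as descriptive within-patient differences or from a model without period terms. It cannot come from the model above. Label it non-randomized and exploratory, as the protocol does, and state the confounding with period 3.

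**If all three are randomized in balanced order:** keep the three-level model, add period and sequence terms, and list the sequences.

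**Cost:** a few model terms and relabelling, with no new data. On the fixed-third reading, the ERP comparison no longer counts as randomized evidence and the preference rule is reworded to one comparison. NIH agreement may be needed, since Milestone 1.5 requires design deviations to be agreed with NIH beforehand.

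### SA 2.3 puts patient preference into a linear Proc Mixed model, but votes and ranks sum to a constant within patient; the usual random-intercept fit then gives 8-14% type I error on the preference comparison, not 5%

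*SAP*

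**What the plan says.** SAP, Statistical Analyses, SA2, on SA 2.3: "The primary statistical analysis will use Proc Mixed in SAS with active contact groupings". The groupings are "1) conventional DBS, (2) multiple active contacts selected based on behavior, and (3) multiple active contacts based on ERPs", entered "as factor and patient preference and changes in PDQ-39 and UPDRS part 3 as data". Preference is therefore a response variable in a linear mixed model, named ahead of the other two.

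The documents describe preference in two forms. The SAP's sample-size text for SA2 speaks of a vote: "using a binomial distribution based on patient preference (vote), PDQ-39, and UPDRS part 3". Protocol item 16.a has patients asked at study conclusion "to rank the programming strategies from the crossover study from best to worst", and its paragraph on the exploratory electrophysiology-guided arm repeats the ranking. Neither document describes a separate preference score given to each condition.

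For SA 2.3 the SAP does not say how preference is coded, whether patient is a random or fixed effect, or which covariance structure applies. Nesting within person is written only for SAs 2.1 and 2.2.

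The SAP also gives preference a second analysis. The criterion is that "20 or more of the 30 participants favor either current steering approach over conventional DBS", with the comment "This would achieve a p value of < 0.049". It continues: "We will declare current steering DBS to be clinically superior to conventional therapy based on patient preference if 20 or more patients meet this criterion".

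**The concern.** A linear mixed model for repeated measures expects each patient to contribute several values that can vary in overall level. A ranking of three strategies cannot: it always uses 1, 2 and 3 and sums to 6. A single vote coded 0/1 over three strategies always sums to 1. All the variation lies within patients, and any two of a patient's values are correlated at -0.5 when there is no preference.

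A random intercept can represent only zero or positive correlation. Faced with these data it sets the patient variance to zero and treats a patient's three values as independent. The between-patient degrees of freedom carry no variation, yet they are pooled into the error term. The error variance is then too small and the tests reject too often.

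At stake is the preference comparison among the three strategies. SA2's hypothesis includes the choice between behavioural and ERP criteria for selecting contacts. The binomial rule pools the two steering strategies, so for preference Proc Mixed is the only stated test of one against the other.

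**Working it through.** **Inputs.** n = 30 patients and k = 3 strategies (SAP, SA2). Coding: ranks 1-3 (Protocol 16.a) or a 0/1 vote (SAP). Nominal level 5% two-sided; the SAP states this for SA1 only, so it is an assumption for SA 2.3. Null: all orderings, or all three votes, equally likely.

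**The plan's own figure.** P(X ≥ 20) for X ~ Binomial(30, 0.5) is 0.0494, one-sided. This agrees with the stated 0.049 at the printed precision. It belongs to the binomial rule; the SAP gives no error rate for the Proc Mixed fit of preference.

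**Why the error term shrinks.** Let SST be the strategy sum of squares and SSw the rest. The between-patient sum of squares is exactly 0.

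- Within-patient error: SSw / (2(n - 1)) = SSw / 58.
- Random intercept at its zero bound: SSw / (3n - 3) = SSw / 87.
- F is inflated by 87 / 58 = 1.5.

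**Effect on the threshold, ranks.** Each patient's squared deviations from the mean rank of 2 add to 1 + 0 + 1 = 2, so the total is 60 and SSw = 60 - SST. For three untied ranks the Friedman statistic equals SST. The 5% critical value of F(2, 58) is 3.156.

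- Bounded random intercept: (SST / 2) / ((60 - SST) / 87) > 3.156 gives SST > 60 × 3.156 / (43.5 + 3.156) = 4.06.
- Patient fixed: 60 × 3.156 / (29 + 3.156) gives SST > 5.89.
- Friedman: SST > 5.99 (chi-square, 2 df).

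The chi-square tail beyond 4.06 is exp(-2.03) = 13.1%, and beyond 5.89 it is exp(-2.94) = 5.3%. The simulated rates below differ slightly because ranks and votes are discrete.

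**One example.** Rank sums of 50, 65 and 65 give SST = (100 + 25 + 25) / 30 = 5.0. The bounded fit has F = 2.5 / (55 / 87) = 3.95, p = 0.025. With patient fixed, F = 2.5 / (55 / 58) = 2.64, p = 0.080. Friedman gives p = 0.082.

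**Rejection rates with no true preference, n = 30** (200,000 simulated trials; the overall F for votes also by exact enumeration):

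| Test | Votes | Ranks |
|---|---|---|
| Bounded random intercept, overall F | 13.4% | 14.4% |
| Same, pairwise contrast | 9.3-9.8% | 10.7% |
| Same, conventional vs mean of two steering | 8.0% | 9.5% |
| Patient fixed, overall F | 4.8% | 5.5% |
| Patient fixed, pairwise contrast | 5.6% | 4.8% |
| Cochran Q (votes) / Friedman (ranks) | 4.8% | 5.5% |

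If all 40 participants in Protocol item 15.a were analysed, the overall F rates would be 11.9% (votes) and 13.1% (ranks).

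**Compound symmetry (CS) and unstructured (UN) covariance.** With k = 3 the lowest admissible CS correlation is -1 / (3 - 1) = -0.5, exactly the value these data force. For one simulated data set the REML log-likelihood was -24 at correlation 0, 71 at -0.499 and 205 at -0.4999999, so it has no finite maximum. The UN matrix had a smallest eigenvalue of 6e-16, which is singular.

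**The case against.** The strongest reply is that the SAP does not commit to the fit that misbehaves. SA 2.3 names neither a patient effect nor a covariance structure, and Proc Mixed with patient as a fixed effect keeps about 5%. This stands. A reader might infer that the preference test must either run at 10-14% or fail to fit; the documents do not support that, because the outcome depends on choices they leave open. The range is also wider at the lower end: conventional against the mean of the two steering strategies is at 8-10%. But nothing in the SAP selects the fixed-effect form. Its nearest wording, repeated-measures mixed models with data nested within person for SAs 2.1 and 2.2, points towards the random-effect and correlated-error fits that inflate or are singular.

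The second reply is that the preference claim does not depend on Proc Mixed. This also stands. A reader might infer that the declaration of superiority on preference carries a 14% error. It does not: that declaration uses the 20-of-30 count, which the sum constraint does not touch. Whether the null of 0.5 suits that count is a separate question, and nothing here relies on it.

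A third reply is that preference could be scored separately for each condition. An unconstrained rating of that kind gave 4.9% in simulation, but neither document provides for one.

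Nor do the documents support extending the point to the whole primary analysis. PDQ-39 and UPDRS part 3 have no such constraint.

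**Conclusion.** The point holds in a limited form. The SAP names a linear mixed model for preference data that, as collected, sum to a constant within patient, and does not say how to code or fit them. This is more than missing detail, because the customary ways of fitting the named model either inflate the error or are singular.

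The size rests on 30 complete votes or rankings, a nominal 5% level, no true preference, and a random intercept bounded at zero. On those terms type I error is roughly one and a half to three times nominal (8.0% / 5% = 1.6; 14.4% / 5% = 2.9). The consequence is confined to the Proc Mixed comparison of preference across the three strategies.

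**What to change.** In the SA 2.3 paragraph of the SAP:

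- Remove patient preference from the Proc Mixed sentence, and keep Proc Mixed for the changes in PDQ-39 and UPDRS part 3.
- Analyse the exit ranking with a Friedman test, patient as block. Only if it is significant, follow with exact sign tests for the pairwise comparisons, including behaviour-guided against ERP-guided steering.
- State that these tests supplement the 20-of-30 rule and do not replace it, so that preference does not have two unconnected analyses.

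The cost is one or two SAP sentences. The ranking is already collected, so no new data, visits or participants are needed.
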